## 14. Provisions to Monitor the Data to Ensure the Safety of Subjects

An independent Investigator Monitor will review all data captured for the study including unanticipated events. This will allow us to assess whether more frequent monitoring will need to take place and how it will affect others currently enrolled. The Investigator Monitor will have the authority to recommend stopping the study early or modifying the study design for safety concerns. He/she will review source documents and compare them for accuracy against data currently collected. The Investigator Monitor will meet with the Principal Investigator to discuss the progress of the patients enrolled in the study. The Investigator Monitor will review the progress of the study within 2 weeks after the first patient is randomized into the study. The Investigator Monitor and the Principal Investigator will conduct monitoring visit approximately every 3 months thereafter. The Investigator Monitor will terminate the study if the safety, welfare and health of patients is jeopardized due to conducting the study according to protocol. Unanticipated events will be reported by the research team to the Investigator Monitor

# DIDIT: Diuretic/Cool Dialysate Trial

and the IRB within 24 hours of becoming aware of the event. The investigators must assess the adverse event (AE)/serious adverse event (SAE) relationship to the hemodialysis frequency, the diuretic and/or iohexol. The research team will also be responsible for preparing and submitting the reports. Every effort will be made to protect subject confidentiality throughout the study. In order to preserve privacy of study data, a series of security procedures will be undertaken which are routinely used by UNM. All information will be kept confidential, and paper patient data will be maintained in a secure location under lock and key. Data collected from study evaluations will be identified by study identification codes, and only numeric identifiers will be stored in the databases. No data element that alone or in combination can identify specific individuals will be entered. Identifying features including names, Social Security Numbers, and address may be provided to the PI or research assistant (RA), but will not be available to the database or the analyst. Any identifying data will be kept in a secure locked file by the PI and RA separate from the study database. Through the use of the security measures available with our hardware and software, access to information will be restricted on a 'need-to-know' basis.

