# DIDIT: Diuretic/Cool Dialysate Trial

## 1. Objectives

Each year in the United States, approximately 100,000 people start maintenance dialysis therapy suffering high mortality rates, frequent hospitalizations, and marked decline in quality of life. The overarching aim of the “**Diuretic/Cool Dialysate Trial**” (DIDIT) is to improve outcomes of incident hemodialysis (HD) patients by recognizing the importance of residual renal function (RRF). This pilot study will demonstrate the feasibility of loop diuretic (bumetanide) use and/or cool dialysate, and will obtain preliminary information that will inform future examination into whether these interventions will slow the rate of RRF decline in HD, improve quality of life, and reduce overall mortality.

The proposed pilot study challenges the current widespread paradigm of discontinuing loop diuretics when initiating chronic HD and/or maintaining the dialysate at a constant temperature of 37 °C for all patients.

**Specific Aim:** We aim to conduct a pilot randomized controlled trial (RCT) to assess feasibility and safety, and to inform the design of a full-scale trial of bumetanide and/or cool dialysate using a two-by-two factorial design, compared to usual care.

The long-term goals of this proposed work are to optimize survival, health-related quality of life (HRQOL) and other outcomes of HD patients by providing them a low dose of a loop diuretic and by lowering the dialysate temperature at the start of their transition to dialysis therapy. The design will permit a rapid scaling-up of the interventions to a larger clinical trial since the incremental dialysis prescription takes advantage of resources and personnel that are readily available. This pilot study will substantially accelerate our ability to address fundamental issues in the care of this population, which is burdened by low HRQOL and can change the current paradigm and practice pattern.

**Hypothesis:** Use of bumetanide and/or cool dialysate during the first six months of HD will slow the rate of RRF decline, decrease inflammation and oxidative stress, improve HRQOL and decrease mortality. To explore this hypothesis we propose to conduct a pilot RCT.

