### **3. Study Design**

This pilot RCT will demonstrate the feasibility and safety of performing a large scale study of diuretic use and/or cool dialysate by examining recruitment, retention, and key outcomes. This study will further assess whether the use of a diuretic compared to non-use of a diuretic (placebo) and/or the use of cool dialysate (35.5 °C) compared to 37 °C for up to 6 months will improve RRF, improve HRQOL and reduce hospitalizations. by randomizing 20 chronic hemodialysis patients from DCI centers in the greater Albuquerque area, to either bumetanide and cool dialysate randomized in a two-by-two factorial distribution.

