# DIDIT: Diuretic/Cool Dialysate Trial

No Diuretic (placebo) and 37°C dialysate	No Diuretic (placebo) and 35.5°C dialysate
Diuretic and 37°C dialysate	Diuretic and 35.5°C dialysate

The study sample will be selected using an approach to limit drop-out while enhancing generalizability and the main analysis will be intention-to-treat. *Considering the intervention cannot be double-blinded, we have made efforts to reduce bias by using objective outcomes and blinding the assessment of patient-reported outcomes.* Subjects will be recruited for 18 months. An additional 6 month period will be used to complete the intervention in the last subjects and they will be re-assessed at month 8 for an end of study evaluation. The recruitment and participation parameters for development of this formal RCT will assess whether the large scale study can meet enrollment criteria and target timelines, and whether patients can be maintained on the study protocol without safety concerns.

In this pilot study we will assess as primary patient outcomes:

- The change in RRF over 6 months
- The association of cool dialysis and/or diuretic with inflammation
- The association of cool dialysis and/or diuretic use with acute kidney injury (AKI) biomarkers.

The secondary patient outcomes will be:

- Change in HRQOL
- Time to first-hospitalization.

Being a pilot study, our focus is on assessing whether changes in RRF can be detected with the proposed technique (urinary creatinine and urea clearance). Biomarkers of inflammation and AKI will be collected to supplement the functional measurement of renal filtration and as surrogate biomarkers of benefit or safety (e.g. nephrotoxicity) that can be monitored in the large scale study.

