### **Exclusion Criteria:**

- Age  $<$ 18 years of age.
- RRF  $<$ 2 mL/min/1.73 m^2 as determined by 24-hour urine collection.
- Allergy or contraindication to bumetanide.
- Expectation that native kidneys will recover.
- History of poor adherence to treatment.
- Unable to verbally communicate.
- Requires more than 3 HD treatments per week due to medical co-morbidity (such as, but not limited to: severe volume overload requiring frequent HD e.g. in systemic oxalosis, or requiring total parenteral nutrition).
- Scheduled for living donor kidney transplant in the next 6 months.
- Intention to change to peritoneal dialysis, or home HD in the next 6 months.
- Plan to relocate to another center within the next 7-8 months.
- Expected geographic unavailability at a participating HD unit for  $>$ 2 consecutive weeks or  $>$ 4 weeks total during the next 6 months (excluding unavailability due to hospitalizations)
- Post kidney transplantation

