## 12. Study Procedures

**Table 1: Schedule of the study tests/assessments/intervention during the pre-trial (4 wks), intervention (24 wks or 6 months) and post-trial periods (4 wks).**

		Study Phases →	p r e	intervention						p o s t	Time to do
	Measurements/Tests	Month →	0	1	2	3	4	5	6	7	
Intervention	Randomization Intervention: (to one of the following arms) 

• Cool dialysate and placebo

• Cool Dialysate and Bumetanide (3mg/day)

• Isothermic dialysate and placebo

• Isothermic dialysate and Bumetanide (3mg/day)

		X								
	Issue (Bumetanide or placebo): For participants whose pre-intervention 24-hour urinary Creatinine and Urea clearance results allow them to complete the study, any current diuretic will be discontinued prior to taking the "study drug".			X			X				During Dialysis
	Bumetanide/placebo compliance check						X		X		
Blood tests & HD Rx	Routine: (Obtain from DCI monthly labs) 

• Albumin (g/dL)

• Hemoglobin (g/L)

• Intact parathyroid hormone (pg/ml)

• Kt/V

• Potassium (mEq/L)

• Calcium (mg/dL)

• Sodium (mEq/L)

• BUN (mg/dL)

• Creatinine (mg/dL)

		X	X	X	X	X	X	X	X	Collect with DCI monthly labs if values are older than 30 days
	Additional blood tests: [Total blood: 11ml: 10ml collected; 1ml waste] 

• B2-microglobulin (drawn pre- and post-HD)

• Cystatin

• NGAL

• KIM-1

• CRP (mg/L)

		X		X			X			Collected with DCI monthly labs

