## 13. Data Analysis

For both studies, patient characteristics and outcomes will be summarized by study arm. Primary outcomes include 6-month change in RRF. Differences between baseline and 6 months will be calculated and analyzed with a mixed model that incorporates potentially important covariates, such as age, gender and ethnicity. For measurements that will be taken monthly, such as albumin, a repeated measures analysis of variance also will be conducted on the measurements rather than the differences. If needed, transformations or analyses based on ranks will be utilized. This approach will also be used for other outcomes that can be treated as continuous variables, such as HRQOL, inflammatory markers and the number of days of hospitalization. For discrete variables, such as the number of hospitalizations, either logistic regression or Poisson regression will be used. The time to first hospitalization will be examined using Kaplan-Meier plots. To adjust for study site and baseline covariates, the proportional hazards model will be used. All analyses will be intent-to-treat, in that patients will be included in analyses regardless of whether the intervention was applied as intended. Estimates of mean change will be obtained along with 95% confidence intervals. All analyses will be conducted in SAS.

This pilot study will inform the design of a larger clinical trial. For Specific Aim 2, the proportions recruited and retained will be estimated. With a recruitment and randomization of 20 patients, the proportion retained can be estimated to within  $\pm 0.18$  with a 95% confidence interval. Estimates of mean changes, along with estimates of variability, will be obtained and used in designing the larger clinical trial.

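### The AE/SAE causality rule names two exposures this trial does not test and leaves out dialysate temperature, one of its two randomized factors

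*Combined protocol and SAP*

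**What the plan says.** The causality instruction is in Section 14, on safety monitoring. It is worded as an obligation: the investigators "must assess the adverse event (AE)/serious adverse event (SAE) relationship to the hemodialysis frequency, the diuretic and/or iohexol". The documents contain no other rule for judging the cause of an adverse event.

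The rest of the protocol describes a trial with different exposures:

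- Section 1 gives the aim of the pilot as "to assess feasibility and safety, and to inform the design of a full-scale trial of bumetanide and/or cool dialysate", in a two-by-two factorial design.
- Section 3 sets out the two comparisons: diuretic against placebo, and "the use of cool dialysate (35.5 °C) compared to 37 °C".
- Table 1 in Section 12 lists four arms, one of which is "Cool dialysate and placebo".
- Section 7 includes preliminary AE and SAE data among the things the study is to deliver.
- Section 18 admits that the effect of the two interventions on hemodialysis complications is not known in either direction. For cool dialysate it adds monitoring of cold intolerance and leaves the investigator to decide whether such symptoms count as a safety endpoint.

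**The concern.** A causality rule should cover what participants are randomized to. This one covers the drug factor and misses the temperature factor, while asking for judgements on two exposures that the trial does not study. An investigator who follows it exactly would record whether a hypotensive episode, an arrhythmia or a death was related to the diuretic, and would have no obligation to say whether it was related to the dialysate temperature.

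The trial itself raises that question. Section 2 justifies cool dialysate partly by an association with less intradialytic hypotension, and the schedule in Section 12 lists hypotensive episodes among the adverse events. The pilot is meant to inform a full-scale trial of both interventions. As written, it would hand on a relatedness record for one of them, and for the other only whatever individual investigators chose to note.

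**Working it through.** No figure in the plan needs to be reproduced. The check is a comparison of the exposures in the Section 14 rule with the exposures in the trial.

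| Exposure | Named in the Section 14 rule | Randomized (Sections 3 and 12) | Where else it appears |
|---|---|---|---|
| Diuretic (bumetanide or placebo) | Yes | Yes | Throughout |
| Dialysate temperature (35.5 °C or 37 °C) | No | Yes | Throughout |
| Hemodialysis frequency | Yes | No | Section 4, as an exclusion: "Requires more than 3 HD treatments per week due to medical co-morbidity" |
| Iohexol | Yes | No | Nowhere |

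**Iohexol.** It is absent from the schedule in Section 12, the risks in Section 18 and the drug information in Section 33. Nor is it needed to measure residual renal function, which Section 3 bases on urinary creatinine and urea clearance.

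**Frequency.** Besides the exclusion criterion, Section 1 refers once, in its long-term goals, to an incremental dialysis prescription. That is not a study arm and no procedure implements it.

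**Counts.**

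- Exposures named: 3. Randomized here: 1. So 3 − 1 = 2 do not apply.
- Randomized factors: 2. Named: 1. So 2 − 1 = 1 is missing.
- Arms: 4. Arms with cool dialysate: 2. Arms in which cool dialysate is the only active intervention: 1 (cool dialysate with placebo).

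**Can the arm comparison stand in for the missing record?** Sections 3 and 13 give 20 randomized patients. The allocation ratio is not stated; assume it is equal, so 10 per temperature level. Suppose, for illustration, that 3 patients have a given SAE, all at one temperature. With the total fixed at 3, the probability that all three fall in one named group is C(10,3)/C(20,3) = 120/1140 = 0.105. The opposite extreme has the same probability, so the two-sided Fisher p is 2 × 120/1140 = 0.21.

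Section 7 gives 25 patients instead of 20. Split 12 and 13, C(25,3) = 2300. If all three events fall in the group of 12, p = C(12,3)/2300 = 220/2300 = 0.10, because the opposite extreme is more probable (286/2300) and is not added. If they fall in the group of 13, p = (286 + 220)/2300 = 0.22. At either sample size, a complete separation of three events would not by itself show an effect of temperature.

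**The case against.** The strongest reply is that little depends on the rule. Nothing in the plan analyses events by relatedness. Rapid reporting in Section 14 is triggered by unanticipated events, not by a causality grade, and the withdrawal criteria in Section 15 do not use relatedness. Section 13 says "patient characteristics and outcomes will be summarized by study arm". Section 14 says "An independent Investigator Monitor will review all data captured for the study including unanticipated events", and the Monitor's power to end the study turns on harm from following the protocol as a whole, which includes dialysate temperature. The schedule collects hypotensive episodes, hospitalizations, deaths and access events in every arm. All of this stands, and it limits the loss to the case-level label. It does not supply the label: collecting an event is not the same as attributing it, and the cold-intolerance provision reaches only cold symptoms.

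Three further points have some weight.

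- Section 3 says the intervention cannot be double-blinded, so a judgement about temperature may be made by staff who know the assignment. That limits the value of the record but does not justify requiring one for the drug alone.
- The 3-versus-0 example is hypothetical. It shows how imprecise the arm comparison is at this size, not that a relatedness field would settle causality.
- The wording may be carried over from another protocol; Section 13 also speaks of two studies and of a second aim that Section 1 does not contain. This is an inference. Whatever its origin, the sentence is the current instruction.

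**Conclusion.** The concern holds. The only causality rule in the documents lists two exposures that the trial does not test and omits one of its two randomized factors. Relatedness to cool dialysate is therefore not a required assessment for any AE or SAE, in a pilot whose aim includes the safety of that intervention.

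The effect is confined to safety attribution. Event collection, the efficacy analyses and the Monitor's oversight are unchanged. The wording comparison rests on no assumption. The p value of 0.21 assumes 20 randomized patients, equal allocation and an illustrative set of three events. The point should be fixed before the safety data are used to plan the larger trial, but it does not threaten the trial's validity.

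**What to change.** Reconcile the sentence in Section 14 with the factors in Sections 3 and 12. Suggested wording: *For each AE and SAE, the investigators must assess the relationship separately to (a) the study drug (bumetanide or placebo) and (b) the dialysate temperature (35.5 °C or 37 °C).*

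Delete hemodialysis frequency and iohexol. Section 5 mentions a protocol modification, and the documents do not show what earlier participants received. If either exposure applied to them, the sentence should say so and limit that assessment to those participants.

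The cost is one sentence and probably one extra field on the adverse event form. The form is not in the documents, so the field is an assumption and may already exist. No visit, procedure or analysis is added, and no dose or clinical rule changes.

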## 15. Withdrawal of Subjects

Subjects may withdraw from this study at any time. Subjects should notify the study PI or staff member of their intent to withdraw in writing. Information collected prior to withdrawal will remain part of the study.

Active treatment with the study interventions will be terminated if the patient:

- Withdraws their informed consent
- Is unable to follow/comply with study procedures
- Undergoes kidney transplantation
- Transfers to home dialysis
- Transfers care to a dialysis facility outside of the Albuquerque DCI clinics or Rio Rancho.
- Becomes pregnant while on study drug.

## 16. Data Management/Confidentiality

For this study, pre-screened eligible patients will be tracked using an ACCESS® database which is stored on a secured UNM HSC network drive. The following PHI is included in this database: subject's name and contact number; patient's emergency contact name and phone number; HD start date; age. This database will be used for study visit scheduling only. Participant name and other identifying information will be linked to a unique study ID once consented. This study ID will not display any information that can identify the participant. All of the data collected from the participant will be coded using participant study ID and kept in a locked cabinet, and/or password protected

## DIDIT: Diuretic/Cool Dialysate Trial

computer files. The master list linking participant identifying information to participant study data will be kept in a separate, secure location at UNM. Only the UNM study team will have access to the master list. We will keep the link between participant identifying information and study data until the end of the research study. This link will only be available to UNM, and will not be accessed by researchers at other institutions.

Participant responses to questionnaires will be kept strictly confidential, and dialysis clinic staff members will not have any knowledge of the patients' answers to these questionnaires.

**Data Management:** The study team will store all study related data and the database secure network servers are sitting behind firewalls and are monitored by network personnel on a 24 h/day, 7 days/week basis. Secure access and training of our data entry staff will be provided by the study team, and confidentiality of data will be carefully maintained. Only study personnel will have access to the secured data.

The investigators will oversee the development of the primary data collection forms. Where applicable, data entry screens in the Web-based program will be constructed in the same format as printed materials. Data entry will be done directly into the REDCap system or similar system at each of the clinical sites. The study staff will coordinate online training on the use of the data entry system, data collection procedures, and patient confidentiality.

Once a patient is recruited and deemed eligible for the study, to initiate inclusion in the web-based tracking system, the University of New Mexico (UNM) will obtain the patient profile (name, participant ID, randomization status and contact information). The tracking system will monitor enrollment, track follow-up rates, and data entry process, and provide up to date status reports. Site coordinators at the clinics will manually enter recruit data into a "firewalled" database via the internet.

Documents will be maintained in a locked area and only necessary research personnel will have access to this information. Only the participant ID number will be entered into the main study database. All research reports, articles, and presentations will present only aggregate study findings, and participants will never be identified by name or any other personal identifier.

Data will be kept for a minimum of 6 years after study completion in line with federal guidelines. PHI and identifiable information will be destroyed 6 years after study closure with UNM HSC HRRC. Non-identifiable information will be destroyed after data analysis is complete.

## **17. Data and Specimen Banking**

Neither data nor specimens will be banked for this study.

# DIDIT: Diuretic/Cool Dialysate Trial

## 18. Risks to Subjects

**Hemodialysis:** may be associated with complications. Hemodialysis can lead to low blood pressure (25% of all dialysis sessions) which may result in abdominal discomfort, nausea, vomiting, muscle cramps, dizziness and anxiety. In addition, hemodialysis can lead to bleeding, tachycardia and other abnormal heart rhythms, electrolyte imbalances, clotting or infection of the vascular access, and rarely, death. ***However, the risks associated with HD would be present whether or not the patient chooses to participate in this study.*** It is unknown whether use of diuretic and cool dialysate will increase or decrease the risk of these complications.

**Cool dialysate (35.5°):** The most common complication for patients dialyzed with cool dialysate is feeling colder, and if severe, they may develop shivering.

Patients will be monitored for patient comfort during dialysis to assess cold intolerance that may occur with cool dialysate. If these symptoms are observed, then the PI will determine whether this is a safety endpoint.

**Bumetanide:** Muscle cramps, severe dizziness, and hearing changes, like ringing in the ears, are the most common side effects of bumetanide (1.1%). A very serious allergic reaction to this drug is also rare.

Patients will be monitored for hypersensitivity reaction or musculoskeletal symptoms to determine tolerability of patients to the diuretic.

**Psychological:** Participants may be asked some questions of a personal nature. They are free to decline to answer any question at any time.

**Loss of Privacy:** Participation in research may involve a loss of privacy. Steps will be taken to mitigate the risk related to confidentiality of study data.

**Pregnancy:** The risk(s) of cool dialysate and/or Bumetanide on a developing fetus are unknown; therefore, subjects who are pregnant or actively planning to become pregnant in the next 8 months will not be allowed to participate in this study.

Subjects of child-bearing potential will have a pregnancy blood test done prior to study randomization. Subjects that refuse pregnancy testing will not be allowed to participate in this study.

**Nursing Mothers:** It is not known whether Bumetanide is excreted in human milk. Breast feeding should not be undertaken while the participant is on this drug. Breast feeding females will not be allowed to participate in this study.

**Hemodialysis Access Site Blood Draws:** Infection, bleeding, and damaging the HD access site.

